3.0 STUDY OBJECTIVES

3.1 Primary Objective

To prospectively compare the overall survival (OS) of patients aged 60-75 who undergo HSCT for MDS (Group A) to that of patients aged 60-75 who do not undergo HSCT (Group B) but who have disease of sufficiently high enough risk to warrant HSCT and who are also fit enough to undergo the procedure (**primary outcome**).

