3.2 Secondary Objectives

1. To prospectively compare the progression-free survival (PFS) of patients in Group A to that of patients in Group B as defined above (**secondary outcome**).
2. To prospectively compare changes in the quality of life (QoL) from baseline to two years of patients in Group A to that of patients in Group B as defined above (**secondary outcome**).

3. To assess the potential association of patient- and disease-specific factors—including International Prognostic Scoring System (IPSS) score, WHO-based Prognostic Scoring System (WPSS) score, number of cytopenias, transfusion dependence, disease duration at baseline, prior therapies and age at HSCT—with the primary and secondary outcomes.

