- d. Seemingly sufficient baseline cardiac function to undergo HSCT (no echocardiogram required).
- e. Seemingly sufficient baseline pulmonary function to undergo HSCT (no pulmonary function tests required).
- f. Seemingly sufficient neuro-psychiatric function to undergo HSCT (no specific neuro-psychiatric evaluation required).

6. Willingness to undergo HLA-typing and consider subsequent HSCT.
7. Willingness and ability to give informed consent.

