5.0 STUDY DESIGN AND METHODS

5.1 Data Collection

Data for this study will be collected using the existing mechanisms of the Dana-Farber/Harvard Cancer Center (DF/HCC) Leukemia Clinical Research Information Systems (Leukemia CRIS) for baseline data (all study participants). For patients who do not go on to HSCT, Leukemia CRIS will be used to collect their outcomes, while HSCT patients will have outcomes collected in the Center for International Blood and Marrow Transplant Research Stem Cell Therapeutic Outcomes Database (CIBMTR SCTOD). Leukemia CRIS is a state-of-the-art information infrastructure for hematologic oncology at the DF/HCC, developed to link clinical outcomes to blood and tissue samples, and to lay the foundation for innovative pilot studies and health services research. The database has been accruing data since January of 2006. Patients in Leukemia CRIS have baseline information and a new patient survey entered at 3 months; they are then assessed for outcomes every 6 months for 3 years. After 3 years, their records are updated for outcomes once per year. Note that baseline IPSS, WPSS and entry criterion (eg, histology, cytogenetics, or transfusion requirements), or as well as eventual HLA status and donor status will be added to Leukemia CRIS data screens and captured for MDS-TAO patients. Also, QoL will be assessed at baseline and two years with the EORTC-30,³⁷ a validated quality of life instrument, as well as the QUALMS-1, an MDS-specific quality of life instrument being validated by [name] under OHRS protocol 13-346.

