6.6 Secondary Outcomes

Secondary outcomes include PFS and changes in self-reported QoL. PFS is defined as time from enrollment until evidence of progression to acute leukemia (time until increase in marrow or peripheral blasts to >20%). QoL will be assessed via changes between baseline and two-year assessments on the EORTC-30 and QUALMS-1. We also plan baseline assessment of IPSS and WPSS, number of cytopenias, transfusion dependence, disease duration at baseline, prior therapies and age at HSCT. Of note, we have not based our power calculations on these outcomes and covariates due to their exploratory nature.

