6.7 Statistical Analysis Plan

As a patient's status in Group A may be changed during the study from waiting for HSCT to being a HSCT recipient, the effect of HSCT will be assessed in a various ways. Our first approach will be using the Mantel-Byer method.⁴⁰ Mantel and Byer (1974) proposed a modified life table to avoid 'time-to-treatment' bias and to accommodate the transient nature of transplant status. The second approach is to treat patient's transplant status as a time-dependent function, $X=X(t)$, as proposed by Crowley and Hu.⁴¹ In this approach, $X(t)$ is an indicator variable at time t , that is, $X(t)=0$ if the patient has not received the transplant at time t , and 1 if the patient has received the transplant at time t . Age at HSCT will be constructed in a similar manner. Another approach is a landmark analysis at one year after study entry.⁴² We will also explore a combination of a pointwise comparison of survival curves at specified time t and a log-rank test after t , using the method proposed by Logan et al.⁴² The last two approaches are particularly suitable as the overall survival between the two groups is not expected to be different during the first year of study, but instead start to separate after approximately one year.

QoL will be assessed using the EORTC-30³⁷ and the QUALMS-1, a disease-specific measure developed by [name] and colleagues at DFCI which is currently undergoing validation.³⁸ The predictability of IPSS or WPSS score on survival outcome will be assessed using the time-dependent ROC curve estimation for censored survival data (survival ROC), proposed by Heagerty et al.⁴⁴⁻⁴⁵ The predictability of these two scoring systems will be compared in each group. In addition, a subset analysis will be performed for Group A (HSCT) to prospectively determine if disease- or patient-related factors predict outcomes of HSCT for MDS in patients aged 60-75. These factors include baseline age at HSCT, IPSS score, WPSS score, number of cytopenias, transfusion dependence, disease duration, prior therapies, and Sorror co-morbidity index. In this subset analysis, standard time-to-event analysis as well as competing risks data analysis⁴⁶ will be performed.

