APPENDIX A: Sample of Baseline Data Abstracted in Leukemia CRIS

1. Data from the New Patient Survey

Reason for Seeking Care
Other Therapies
Quality of Life
Medical Hx
Demographics
Pt Status
Cancer Hx
Tobacco Hx
Social History
Household Members
Family Hx

2. Data abstracted from Medical Record

Demographics
Patient Disease and morphology
Episode
Diagnosis Detail
Pt Status
Sites of Involvement
Lab Results and tests
BCR-ABL:
FLT-3 AL (D835 mutation)
FLT-3 ITD
Hematocrit
JAK-2
Malignant Cells in Blood
Malignant Cells in BM aspirate
Malignant Cells in BM Biopsy
NPM-1:
Platelet Count
RAR-Alpha
White Blood Cell Count
Cytogenetics
t (1;19)
t (4;11)
t (6;9)
t (8;14)
t (8;21)
t (9;11)
t (9;22)
t (11;14)
t (14;18)
t (15;17)

*t (16;16)
Hyperdiploid
abn 3q:
abn 13q*

*abn 17p
abn 21q
del 5q:
monosomy 5
del 7q/monosomy 7
del 9q
del 11q
del 12p
del 17 p
del 20q
inv 16
trisomy 6
trisomy 8
trisomy 12
trisomy 21
trisomy 22*

*Normal karyotype
Other: other cytogenetic events not listed above
Other abnormalities: other chromosomal abnormalities not listed
Multiple complex abnormalities:
Not Performed
Inconclusive Results*

Hospitalizations

Treatments

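### No comorbidity index score is scheduled for Group B or timed for Group A, although the non-randomised OS comparison presumes that Group B was fit enough for HSCT

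*Combined protocol and SAP*

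**What the plan says.** The primary objective (3.1) compares OS in patients who undergo HSCT with OS in patients who do not, but "who are also fit enough to undergo the procedure". Under 4.1, every enrollee must have ECOG 0 to 2 and meet limits for bilirubin, AST/ALT and creatinine. The cardiac criterion reads "Seemingly sufficient baseline cardiac function to undergo HSCT (no echocardiogram required"; the pulmonary and neuro-psychiatric criteria follow the same pattern. Exclusion 4 in 4.2 leaves severe comorbidity to the principal investigator's judgment.

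Four places bear on which covariates are collected or analysed:

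- Secondary objective 3 (3.2) names IPSS, WPSS and "number of cytopenias, transfusion dependence, disease duration at baseline, prior therapies and age at HSCT".
- Section 5.1, on fields added to Leukemia CRIS for this study, begins "Note that baseline IPSS, WPSS and entry criterion (eg, histology, cytogenetics, or transfusion requirements" and goes on to HLA and donor status.
- Section 6.6 states: "We also plan baseline assessment of IPSS and WPSS, number of cytopenias, transfusion dependence, disease duration at baseline, prior therapies and age at HSCT".
- Section 6.7 states that "a subset analysis will be performed for Group A (HSCT) to prospectively determine if disease- or patient-related factors predict outcomes of HSCT", and its factor list ends "number of cytopenias, transfusion dependence, disease duration, prior therapies, and Sorror co-morbidity index".

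Only the last of these names a comorbidity index, and it covers Group A alone.

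**The concern.** Membership of Group A or B depends on whether a patient goes on to transplant, not on randomisation. The comparison is persuasive only if the groups were of similar fitness at entry, or if differences can be measured and allowed for. Section 2.0 makes the same demand from the policy side: the Medicare coverage route requires recipients to be compared with similar patients who are not transplanted.

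Mantel-Byar, the time-dependent covariate and the landmark analysis in 6.7 deal with when a transplant happens. They do not deal with who is selected for it. If healthier enrollees are more likely to reach HSCT, all three could attribute part of that advantage to the transplant. The plan names an index that would help examine this, but provides for it only in recipients. It also does not say when the index is scored, from what source, or by whom.

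**Working it through.** **The plan's own figures.** No number in the plan is disputed. With time in months, the survival curves in 6.4 give at 60 months:

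- S_A = 0.19 + 0.4 × 2^(−60/10) + 0.41 × 2^(−60/20) = 0.19 + 0.00625 + 0.05125 = 0.2475 (stated 25%).
- S_B = 2^(−60/18) = 0.099 (stated 10%).

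With 290 patients, one third in Group A, 60 months of uniform accrual, 60 months of further follow-up, one-sided alpha 0.025 and no dropout, log-rank power is 85.4% by numerical integration and 83.7% in a 4000-run simulation. The stated figure is 85%. Adding a baseline score changes none of these.

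**Where the index and ECOG appear.**

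| Place | Sorror index | ECOG |
|---|---|---|
| 3.2, secondary objective 3 | no | no |
| 4.1, inclusion criteria | no | yes, as an entry limit |
| 5.1, fields added to CRIS | no | no |
| 6.6, baseline assessments | no | no |
| Appendix A | no | not by name |
| 6.7, Group A subset analysis | yes | no |

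Appendix A is titled "Sample of Baseline Data Abstracted in Leukemia CRIS", so absence there does not prove that an item is not collected. Sections 5.1 and 6.6 carry the point. Apart from the Sorror index, the factors in 6.7 match those in 6.6; the index is the one analysed factor with no collection provision.

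**Patients without a scheduled score.** Inputs are N = 290 and A:B = 1:2 (6.2).

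- Group A: 290 × 1/3 = 96.7, about 97.
- Group B: 290 × 2/3 = 193.3, about 193.
- Share: 193/290 = 67%.

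This counts missing scores. It does not measure bias.

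**What this does to an adjusted analysis.** The time-dependent model in 6.7 has hazard h0(t) × exp(b·X(t)), where X(t) indicates transplant by time t. Allowing for entry fitness means adding terms such as c·(Sorror) + d·(ECOG). The index term needs a value for every enrollee. If only recipients have one, the adjusted model cannot be fitted to about two thirds of the cohort, including everyone never transplanted.

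**Bias.** A figure would need the comorbidity imbalance between the groups and the mortality hazard ratio for comorbidity. The documents give neither, so size and direction remain unknown.

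**The case against.** The strongest reply is that this is one covariate in one subset analysis, that 6.6 calls its outcomes and covariates exploratory, and that other fitness data exist. Eligibility supplies laboratory values and ECOG. The New Patient Survey asks about heart, lung, stroke, diabetes, kidney, liver, rheumatologic and cancer history, and 5.1 makes CRIS the baseline source for all participants. Much of this stands: comorbidity is not wholly unrecorded. But the survey is self-reported, no index is derived from it, and 6.7 does not use it to compare or adjust the groups.

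Four stronger readings are tempting, and the documents do not support them.

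- *Any Group A score would be taken 4-6 months after baseline, at transplant work-up.* No section gives the scoring time. The 4-6 months in 6.4 run from enrollment to the transplant itself. A later score is possible, not established.
- *A pre-HSCT score would be an invalid predictor in Group A.* The subset question is what predicts outcome after transplant, and its list includes age at HSCT. A pre-HSCT score is legitimate there. What is missing is a statement of which score is meant.
- *Comorbidity is a main reason why enrollees do not proceed.* The abstract's examples are lack of a donor and rapid progression, and exclusion 4 applies to everyone at entry. A part played by comorbidity is plausible, but it is an inference.
- *Missing scores could never be recovered.* Section 5.2 plans to obtain and abstract outside hospital records. Later scoring might be uneven, but it is not ruled out.

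**Conclusion.** The point holds as a gap in planned measurement. Under the lists in 5.1 and 6.6, no comorbidity index is scheduled for about 193 of 290 patients, and Group A has no stated scoring time. The primary comparison would then rest on presumed fitness in Group B, with partial data on it and no common comorbidity measure for comparing or adjusting the groups.

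The count assumes the projected 1:2 split. The importance assumes that comorbidity may differ between those who reach HSCT and those who do not, which the documents neither show nor exclude. The gap does not show that the OS comparison is biased; it limits the plan's ability to examine the question. The change is worth making because it is cheap and affects what the study can conclude.

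**What to change.** Add the Sorror index and the ECOG value to the baseline fields in 5.1 and 6.6 for all enrollees. Score the index at study entry from existing records, marking any item without a test on file as not assessed, and state how such items enter the score.

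Report both measures by group. Include both as baseline covariates in a supportive version of the time-dependent Cox model for OS in 6.7. Without that step, the scores would describe the groups but not adjust the comparison.

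For the Group A predictor analysis, state whether the entry score or the pre-HSCT score is used, and keep them as separate variables.

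The cost is a few CRIS fields and modest chart abstraction. Section 7.0 already commits a half-time research assistant in addition to the full-time one on CRIS. No new tests and no change in sample size are needed. The downside is incomplete cardiac and pulmonary items, because those tests are not required at entry.

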7.0 COMMITMENT OF INSTITUTIONAL RESOURCES

MDS-TAO will be a long-term study, with at least 5 years of active accrual, and likely several more years of follow-up. The DFCI has invested a substantial commitment to the success of this effort. The current Leukemia CRIS program has a dedicated 100% FTE clinical research assistant, and is overseen by a disease-specific Principal Investigator, as well as a Population Scientist (2.5% FTE). MDS-TAO will call on these existing resources; in addition, the DFCI has committed support for another 50% FTE research assistant—who will be housed and supervised at the McGraw-Patterson Center for Outcomes and Policy Research—as well as 20% FTE programmer (to start in year 2 of the study) to assist the project biostatistician with interim analyses. Finally, the DFCI will fund or assist with the ascertainment of grant funding for 10%

FTE of the Principal Investigator, who will work to assure the quality of the data collected as well as the scientific integrity of the data and any resulting manuscripts.

8.0 POTENTIAL CLINICAL AND POLICY IMPACT

To our knowledge, our planned analysis will be the first large study of comparative outcomes associated with RIC HSCT versus non-HSCT for older patients with MDS—crucial information for our health care system as our country becomes increasingly concerned with the costs of health care and comparative effectiveness. Our results will provide essential insight to patients and practicing oncologists regarding the advisability of HSCT for MDS patients in this largely understudied age group, as well as help policymakers and funding sources such as CMS understand if the procedures truly lead to improved outcomes. Next, the data we plan to collect regarding potential changes in quality of life associated with HSCT in this age group promise to address an important gap in the current HSCT literature. Finally, MDS-TAO would also provide a long-overdue source of primary and prospective data for MDS researchers as to the usefulness of the IPSS and WPSS in prognosticating for transplantation-related outcomes.

APPENDIX A: Sample of Baseline Data Abstracted in Leukemia CRIS

1. Data from the New Patient Survey

Reason for Seeking Care
Other Therapies
Quality of Life
Medical Hx
Demographics
Pt Status
Cancer Hx
Tobacco Hx
Social History
Household Members
Family Hx

2. Data abstracted from Medical Record

Demographics
Patient Disease and morphology
Episode
Diagnosis Detail
Pt Status
Sites of Involvement
Lab Results and tests
BCR-ABL:
FLT-3 AL (D835 mutation)
FLT-3 ITD
Hematocrit
JAK-2
Malignant Cells in Blood
Malignant Cells in BM aspirate
Malignant Cells in BM Biopsy
NPM-1:
Platelet Count
RAR-Alpha
White Blood Cell Count
Cytogenetics
t (1;19)
t (4;11)
t (6;9)
t (8;14)
t (8;21)
t (9;11)
t (9;22)
t (11;14)
t (14;18)
t (15;17)

*t (16;16)
Hyperdiploid
abn 3q:
abn 13q*

*abn 17p
abn 21q
del 5q:
monosomy 5
del 7q/monosomy 7
del 9q
del 11q
del 12p
del 17 p
del 20q
inv 16
trisomy 6
trisomy 8
trisomy 12
trisomy 21
trisomy 22*

*Normal karyotype
Other: other cytogenetic events not listed above
Other abnormalities: other chromosomal abnormalities not listed
Multiple complex abnormalities:
Not Performed
Inconclusive Results*

Hospitalizations

Treatments

APPENDIX B: New Patient Survey for Leukemia CRIS, including EORTC-30

APPENDIX C: QUALMS-1 Quality of Life Instrument

APPENDIX D: Consent Form for MDS-TAO

Hematologic Oncology New Patient Survey

Patient Name	Age	D.O.B.
DFCI MRN	BWH MRN	MGH MRN
Appt Provider	Appt Date/Time	

Please fill out this form and return it to the
MAIN RECEPTION DESK

Please complete this form as thoroughly as possible. This information will help your health care providers to develop a plan of care tailored to your needs.

Thank you.

REASON FOR SEEKING CARE**Where were you first diagnosed with your blood disorder?**

Select ONE.

- Emergency Room
- Hospital
- Hematologist/Oncologist's office
- Primary Care Physician
- Other physician office
- Other

Have you seen another physician for your current blood disorder?

- No
- Yes

If yes, what type of physician(s) have you seen previously for the treatment or evaluation of your current blood disorder?

Select ALL that apply.

- Medical oncologist (treats with chemotherapy / medicines)
- Primary care physician
- Radiation oncologist (treats with radiation)
- Other (Please specify: _____)

REASON FOR SEEKING CARE (continued)

Have you received any prior treatments for your blood disorder?

No Yes

If yes, what prior treatments have you received?

Select **ALL** that apply.

- Chemotherapy
- Radiation therapy
- Surgery
- Vaccine therapy
- Other (Please specify: _____)

Who recommended that you to come to DFCI/MGH for consultation?

Select **ALL** that apply.

- Children
- Friend
- Internet
- My oncologist
- My primary care physician
- Self
- Spouse
- Other family
- Other (Please specify: _____)

Why are you coming to clinic today?

Select **ALL** that apply.

- To find out whether I have a blood disorder
- To see if I'm eligible for a clinical trial
- To find out if there are any new treatments available
- Other (Please specify: _____)

Do you expect to receive your ongoing care at DFCI/MGH?

Select **ONE**.

- No- I'm here for a second opinion
- Yes
- Not sure

REASON FOR SEEKING CARE (continued)

Outside of a multivitamin do you REGULARLY do other complementary/nontraditional/alternative therapies?

No Yes

If yes, which therapies? Select **ALL** that apply.

 Acupressure	 Macrobiotics	 Tai Chi or Chi Gong
 Acupuncture	 Massage	 Yoga
 Biofeedback	 Meditation	 Other (please specify _____)
 Body Work	 Megavitamins	
 Herbal and botanical remedies	 Reiki	
 Hypnosis	 Spiritual healing	

QUALITY OF LIFE

We are interested in some things about you and your health. Please answer all of the questions by circling the number that applies to you.

	Not at All	A Little	Quite a Bit	Very Much
Do you have any trouble doing strenuous activities, like carrying a heavy shopping bag or a suitcase?	1	2	3	4
Do you have any trouble taking a long walk?	1	2	3	4
Do you have any trouble taking a short walk?	1	2	3	4
Do you need to stay in bed or a chair during the day?	1	2	3	4
Do you need help with eating, dressing, washing yourself or using the toilet?	1	2	3	4

1. **What is the primary purpose of the study?**

1. **What is the primary purpose of the study?**

1. **What is the primary purpose of the study?**

QUALITY OF LIFE (continued)

During the past week:	Not at All	A Little	Quite a Bit	Very Much
Were you limited in doing either your work or other daily activities?	1	2	3	4
Were you limited in pursuing your hobbies or other leisure time activities?	1	2	3	4
Were you short of breath?	1	2	3	4
Have you had pain?	1	2	3	4
Did you need to rest?	1	2	3	4
Have you had trouble sleeping?	1	2	3	4
Have you felt weak?	1	2	3	4
Have you lacked appetite?	1	2	3	4
Have you felt nauseated?	1	2	3	4
Have you vomited?	1	2	3	4
Have you been constipated?	1	2	3	4
Have you had diarrhea?	1	2	3	4
Were you tired?	1	2	3	4
Did pain interfere with your daily activities?	1	2	3	4
Have you had difficulty in concentrating on things, like reading a newspaper or watching television?	1	2	3	4
Did you feel tense?	1	2	3	4
Did you worry?	1	2	3	4
Did you feel irritable?	1	2	3	4
Did you feel depressed?	1	2	3	4
Have you had difficulty remembering things?	1	2	3	4
Has your physical condition or medical treatment interfered with your family life?	1	2	3	4
Has your physical condition or medical treatment interfered with your social activities?	1	2	3	4
Has your physical condition or medical treatment caused you financial difficulties?	1	2	3	4

For the following questions please circle the number between 1 and 7 that best applies to you.

How would you rate your overall health during the past week?

A horizontal scale with seven numerical tick marks from 1 to 7. The first tick mark is labeled 'Very poor' and the last tick mark is labeled 'Excellent'.

How would you rate your overall quality of life during the past week?

A horizontal scale with seven numerical tick marks from 1 to 7. The first tick mark is labeled 'Very poor' and the last tick mark is labeled 'Excellent'.

QUALITY OF LIFE (continued)

Which option below describes your level of physical activity OVER THE PAST WEEK?

Select **ONE**

- Fully active, able to carry on all usual activities without restriction
- Restricted in strenuous activity; can walk; able to carry out light housework
- Can walk and care for self; up more than $\frac{1}{2}$ day
- Need some help taking care of self; spend more than $\frac{1}{2}$ day in bed or chair
- Cannot take care of self at all and spend all of my time in bed or chair

MEDICAL HISTORY

Have you ever had a heart attack?

No Yes

Have you ever been treated for heart failure (you may have been short of breath and the doctor may have told you that you had fluid in your lungs or that your heart was not pumping well)?

No Yes

Have you ever had an operation to unclog or bypass the arteries in your legs?

No Yes

Have you had a stroke, cerebrovascular accident, blood clot or bleeding in the brain, or transient ischemic attack (TIA)?

No Yes

If yes, do you have difficulty moving an arm or leg as a result of a stroke or cerebrovascular accident?

No Yes

Do you have asthma, emphysema, chronic bronchitis, or chronic obstructive lung disease?

No Yes

If yes, do you take medicine for your condition (either on a regular basis or just for flare-ups)?

No Yes

Do you have stomach ulcers or peptic ulcer disease?

No Yes

If yes, was this condition diagnosed by endoscopy (where a doctor looks into your stomach through a scope) or an upper GI or barium swallow study (where you swallow chalky dye and then x-rays are taken)?

No Yes

Do you have diabetes or high blood sugar?

No Yes

If yes, answer all of the following four questions:

- is it treated by modifying your diet? No Yes
- is it treated by medications taken by mouth? No Yes
- is it treated by insulin injections? No Yes
- has your diabetes caused problems with your kidneys or problems with your eyes (treated by an ophthalmologist)? No Yes

MEDICAL HISTORY (continued)

Have you ever had problems with your kidneys? No Yes

If yes, have you had poor kidney function with blood tests showing:

high creatinine levels? No Yes

have you used hemodialysis or peritoneal dialysis? No Yes

have you received a kidney transplant? No Yes

Do you have rheumatoid arthritis? No Yes

If yes, do you take medications for it regularly? No Yes

Do you have lupus (systemic lupus erythematosus) or polymyalgia rheumatica? No Yes

Do you have any of the following conditions?

Alzheimer's Disease or another form of dementia? No Yes

Cirrhosis or serious liver damage? No Yes

AIDS? (This question is optional.) No Yes

Leukemia or polycythemia vera? No Yes

Lymphoma? No Yes

Cancer (other than skin cancer, leukemia or lymphoma)? No Yes

If yes, has the cancer spread or metastasized to other parts of your body? No Yes

Have you received a heart, lung, liver or pancreas transplant? No Yes

Do you have any other autoimmune disease (besides lupus or polymyalgia rheumatica)?

If so, what kind? _____ No Yes

Do you have a history of immunodeficiency? No Yes

If yes, please elaborate _____

Have you ever tested positive for HIV? (This question is optional) No Yes

If yes, have you ever received antiviral treatment? No Yes

Have you ever tested positive for hepatitis B? No Yes

If yes, have you ever received treatment? No Yes

Have you ever tested positive for hepatitis C? No Yes

If yes, have you ever received treatment? No Yes

Were you told that you have Helicobacter pylori (either during an endoscopy or by blood test)? No Yes

Do you have either Crohn's disease or ulcerative colitis? No Yes

Do you have celiac sprue? No Yes

PATIENT BACKGROUND INFORMATION

For research purposes only, we would like to know the following information.

Are you of Spanish / Hispanic origin?

- No
- Yes
- Not sure

What best describes your racial background? Select ALL that apply.

Definitions from Federal Government's Office of Management and Budget

	American Indian or Alaskan Native	Have origins in any of the original peoples of North and South America (including Central America) and maintain tribal affiliation or community attachment
	Asian	Have origins in any of the original peoples of the Far East, Southeast Asia, or the Indian subcontinent including for example, Cambodia, China, India, Japan, Korea, Malaysia, Pakistan, the Philippine Islands, Thailand and Vietnam
	Black or African American	Have origins in any of the original peoples of Africa: includes Haitian
	Native Hawaiian or Other Pacific Islander	Have origins in any of the original peoples of Hawaii, Guam, Samoa, or other Pacific Island
	White	Have origins in any of the original peoples of Europe, the Middle East or North Africa

What best describes your educational status?

Select ONE

- Some grade school
- Some high school
- High school graduate
- Vocational or technical school
- beyond high school
- Some college or associate's degree
- College
- Graduate or professional school
- Other (Please specify _____)

What is your current employment status?

Select ONE

- Disabled
- Employed 32 hours or more per week
- Employed less than 32 hours per week
- Full time student
- Homemaker
- On medical leave
- Part time student
- Part time student and also employed less than 32 hours per week
- Retired
- Unemployed and/or seeking work
- Other (Please specify _____)

PATIENT BACKGROUND INFORMATION(continued)

What is your current weight? pounds

What was your weight 6 months ago? pounds

What is your current height? feet inches

PAST CANCER HISTORY

In the past, have you ever had any of the following types of cancer listed below? Check ALL that apply (do not include basal cell skin cancer).

For each of the cancers checked, what type of treatment did you receive for it? Check ALL that apply.

Cancer diagnosis	Approximate diagnosis date	Chemotherapy	Surgery	Radiation Therapy	Hormone Therapy
 Bladder					
 Brain					
 Breast					
 Colon					
 Colorectal					
 Hodgkin's lymphoma					
 Invasive cervical					
 Kidney					
 Leukemia					
 Liver					
 Lung					
 Lymphoma, type unknown					
 Melanoma					
 Mouth/throat					
 Multiple Myeloma					
 Non-hodgkin's lymphoma					
 Ovarian					
 Pancreatic					
 Prostate					
 Rectal					
 Stomach					
 Thyroid					
 Uterine/Endometrial					
 Other (Please Specify _____)					

1. **What is the primary purpose of the study?**

1. **What is the primary purpose of the study?**

TOBACCO HISTORY

Have you ever smoked more than 100 cigarettes in your lifetime? **O No** **O Yes**

If Yes...

How old were you when you started smoking cigarettes?

Throughout the time that you smoked cigarettes, what is the average number of cigarettes per day that you smoked?

Age started

Do you currently smoke cigarettes (within the past month)?

No Yes

If No...

What was the date that you stopped smoking cigarettes?

□ □ / □ □ / □ □ □ □

SOCIAL HISTORY

Have you ever or do you currently drink alcohol?

Select **ONE**

- No, never
- Yes, but only in the past
- Yes, currently

How many alcoholic beverages (beer, wine, mixed drinks, etc) do you consume weekly?

Select ONE

- None
- Less than 1 drink per week
- 1- 4 drinks per week
- 5-9 drinks per week
- 10-19 drinks per week
- More than 19 drinks per week

If your alcohol intake in the past was different from now, how many alcoholic beverages (beer, wine, mixed drinks, etc) did you consume weekly?

Select ONE

- None
- Less than 1 drink per week
- 1- 4 drinks per week
- 5-9 drinks per week
- 10-19 drinks per week
- More than 19 drinks per week

HOUSEHOLD MEMBERS

Please list the age of all the people who live with you and their relationship to you. Please include all people who share your household, whether they are blood relatives or not (see key below). If there is more than one person with a particular relationship to you, please assign each a number (e.g. Son 1 Son 2).

No household members

Household Member	Age

Key:		Household Members
Aunt	Grandson	Personal Care Assistant
Brother	Housekeeping Staff	Roommate
Cousin	Husband	Significant Other
Daughter	Mother	Sister
Father	Nanny	Son
Granddaughter	Nephew	Tenant
Grandfather	Niece	Uncle
Grandmother	Nurse	Wife
Other (Please Specify _____)		

FAMILY HISTORY

Please include only blood relatives, both living and deceased.

How many sisters do you have?

How many brothers?

How many daughters?

How many sons?

FAMILY HISTORY (continued)

Do you have any blood related relatives who have been diagnosed with cancer? If yes, please use the chart below to indicate their relationship to you, the type of cancer they have, their age at diagnosis, and whether or not they are still living.

NOTE: If you have more than one relative of a particular type who has been diagnosed with cancer, please assign each a number in the relative column. E.g. Sister 1 and Sister 2

*For example if your mother was diagnosed with stomach cancer at age 63 and she is still living, you would print Mother in the Relative column, Stomach in the Cancer Type column, 63 in the Age at Diagnosis column and check off Yes in the Alive column. If you only know that she was diagnosed sometime in her 60's, you would print 60 in the Age at Diagnosis column and check off Yes in the Age Estimated to the Decade Column.

Blood Relative	Maternal/ Paternal/Both	Cancer Type	Age at Diagnosis	Is Age Estimated to the decade?	Alive?
Sample Mother	M	Stomach Cancer	63	 Yes	 Yes  No  Not Sure

* Relatives

Aunt Mother
Brother Sister
Cousin Son
Daughter Uncle
Father Other (Please
Grandfather specify _____)
Grandmother

Bladder
Brain
Breast
Colon
Colorectal
Hodgkin's lymphoma
Invasive Cervical
Kidney

** Cancer Types

Leukemia	Pancreatic
Liver	Prostate
Lung	Rectal
Lymphoma, type unknown	Stomach
Melanoma	Thyroid
Mouth/throat	Uterine/Endometrial
Multiple Myeloma	Unknown
Non-Hodgkin's Lymphoma	Other (Please specify _____)
Ovarian	

In order to facilitate correspondence with you and your physicians please confirm the following information and correct if necessary.

Patient:

Name: _____

Name: _____

Address: _____

Address: _____

Home Phone: ()_____

Home Phone: ()_____

Work Phone: ()_____

Work Phone: ()_____

Marital Status: _____

Marital Status: _____

Referring physician:

Name: _____

Name: _____

Address: _____

Address: _____

Phone: ()_____

Phone: ()_____

Primary Care physician:

Name: _____

Name: _____

Address: _____

Address: _____

Phone: ()_____

Phone: ()_____

Q.U.A.L.M.S.-1

© Dana-Farber Cancer Institute, Boston, MA

The Quality of Life in Myelodysplasia Scale

Patients often have different experiences over the course of their illness; however, please limit your responses to your experience over the past week only. The information you provide will remain strictly confidential.

During the past week, how often...		Never	Rarely	Sometimes	Often	Always
1	...did you feel as though there was a lack of clear information about your disease?					
2	...have you felt there was limited emotional support available for patients with MDS beyond their families?					
3	...did you feel as though you couldn't do anything about your disease?					
4	...did you feel the course of your disease was unpredictable?					
5	...did you have difficulty explaining MDS to your friends or family?					
6	...did you have trouble concentrating?					
7	...have you considered changing long-term plans due to health concerns?					
8	...have you experienced shortness of breath?					
9	...did low energy levels cause you to change your schedule?					
10	...did you feel as though your life was organized around medical appointments?					
11	...have you felt a sense of hopelessness?					
12	...have you been worried about getting an infection?					
13	...have you had sufficient energy for routine tasks?					
14	...were you afraid of dying?					
15	...did you feel angry about your diagnosis?					
16	...were you worried about bleeding?					
17	...did you feel a sense of gratitude for a part of life that you took for granted before?					
18	...did you feel nauseated?					
19	...did you worry about your MDS progressing or developing into leukemia?					
20	...did you take into account that you might be fatigued when planning your activities?					

For the following questions, please again mark the answer choice that best represents your experiences and feelings over the past week. The information you provide will remain strictly confidential.

During the past week, how often...		Never	Rarely	Sometimes	Often	Always
21	...were you concerned that your MDS caused a financial burden for you or your family?					
22	...did you feel your family relationships were strained by your disease?					
23	...have you felt weak?					
24	...have you been too tired to take on the responsibilities you used to have?					
25	...did you worry about becoming a burden to your friends or family?					
26	...were you unable to participate in activities you are used to doing?					
27	...have you felt anxious about test or lab results?					
28	...did you avoid crowds because of fear of getting an infection?					
29	...did you find yourself grateful for tomorrow?					
30	...did you feel you were able to find quality information about MDS treatments?					
31	...were you concerned about bruising?					
32	...did you feel as though there were a lack of concrete answers about what will happen with your MDS?					
33	...did you experience a change in bowel habits?					

For the following questions, **you may select “not applicable”** if the question does not apply to you.

During the past week, how often...		Never	Rarely	Sometimes	Often	Always
34	...were you afraid of losing your job? (check here  if not applicable because you are unemployed/retired)					
35	...did you feel too tired to drive? (check here  if not applicable because you do not drive)					
36	...were you afraid to have sex due to your blood counts? (check here  if not applicable because you are not currently sexually active)					
37	...were you afraid that your MDS treatment would stop working? (check here  if not applicable because you are not currently being treated)					
38	...have you been too tired to take care of a family member or loved one? (check here  if not applicable because you are not providing such care)					

*Thank you for completing
the QUALMS-1.*
